8.1 Adverse reactions

The most common adverse reactions (≥10%) are liver problems, photosensitivity, rash, abdominal pain, nausea, vomiting, diarrhea, dyspepsia, fatigue, headache, dizziness, anorexia, sinusitis, insomnia, weight loss, and arthralgia. These possible adverse events are documented in the informed consent.

Management of abnormal liver function tests

Elevated ALT, AST, and bilirubin elevations have occurred with pirfenidone and will be monitored monthly as above. The investigator will monitor patients for toxicities.

The following protocol will be followed for management of elevation in AST, ALT, and total bilirubin:

Magnitude of AST or ALT elevation	Recommendation
3 to 5 x ULN	Confounding medications should be discontinued if clinically indicated, other causes excluded, and the patient monitored closely. The dose of study treatment may be reduced or interrupted if clinically appropriate, with subsequent repeat titration to full dose, as tolerated
≤5 x ULN accompanied by symptoms or hyperbilirubinemia (>2x ULN)	Study treatment should be permanently discontinued
>5 x ULN	Study treatment should be permanently discontinued

Management of photosensitivity and rash

Photosensitivity and rash have been noted with pirfenidone. Patients will be instructed to avoid exposure to sunlight and sunlamps. Patients will be instructed to wear sunscreen (sun

protection factor 50 or higher) and protective clothing daily. Temporary dosage reductions or discontinuations may be required.

If a patient experiences significant rash or photosensitivity, treatment of symptoms and/or temporary dose reductions, interruptions, or discontinuation of study treatment should be considered.

Management of gastrointestinal disorders

Nausea, vomiting, diarrhea, dyspepsia, gastroesophageal reflux disease, and abdominal pain have occurred with pirfenidone. Temporary dosage reductions or discontinuations may be required.

Dosage Modification due to Drug Interactions

Ciprofloxacin is a moderate CYP1A2 inhibitor. With the use of ciprofloxacin at a dosage of 750 mg twice daily, reduce pirfenidone to 534 mg three times a day (1602 mg/day).

EKG abnormalities

If the QTc interval is > 550 msec, this should be confirmed with a repeat EKG within 24 hours. The study drug should be interrupted until the repeat EKG reading. If QTc is still >550 msec than cardiology will be consulted and drug discontinued if abnormality persists.

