If the QTc interval is between 500 and 550 msc, confirmed by a repeat EKG within 24 hours, and verified by a local cardiologist, study treatment should be interrupted. If an alternative explanation is identified (electrolyte abnormality or concomitant medication), the study treatment may be re-initiated at the investigator's discretion in consultation with the medical monitor.

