10.3 Primary Endpoint Analysis

We believe the data obtained from our study will provide important radiographic and biological signals regarding the efficacy of pirfenidone. We expect a lower SD as the patient population selected will be much better phenotyped for CLAD presence. The high SD in the preliminary data came from patients who improved over time as this data is derived from patients who had CT scans available as routine care rather than in our study where they will be done prospectively. Furthermore, if fibrotic remodeling by pirfenidone is effective we can potentially even see a decrease in fSAD.

We believe that this CT based novel methodology to evaluate small airway disease will provide us with much stronger signal over 6-month period than FEV1 which reaches a floor effect. So the disease progresses even though FEV1 changes are not very evident ultimately leading to graft failure and death. Furthermore, our ability to isolate mesenchymal cells from BAL offers a first unique scenario to directly study the anti-fibrotic effect of pirfenidone.

This trial will also provide information regarding the tolerance of pirfenidone in a lung transplant population who already take multiple medications with serious possible side effects. Tolerance of pirfenidone in addition to baseline transplant medications will be assessed.

Secondary:

- Change in FEV₁ over 24 weeks by treatment arm (e.g, percent or time weighte)
- Change in FVC over 24 weeks by treatment arm
- Number of subjects with treatment intolerance over 24 weeks
 - Measured by elevated AST, ALT, total bilirubin that results in dose reduction or discontinuing study treatment (the 3 – 5 or greater ULN)
- Number of subjects with Adverse events related to treatment with Pirfenidone
 - Safety of pirfenidone will be measured by adverse events determined to be related to the study drug as determined by the principal investigator through

review of medical history, physical exam and laboratory findings *or be measured by liver and renal function tests, physical exam*

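### Treatment intolerance is defined in section 10.3 by liver tests alone, so drug changes for skin, gastrointestinal and QTc events are missed, and section 10.1 lists different secondary safety endpoints

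*Combined protocol and SAP*

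**What the plan says.** The synopsis and section 4.1 name treatment intolerance as a secondary endpoint without defining it. Section 10.3 repeats the name and gives the only definition: "Measured by elevated AST, ALT, total bilirubin that results in dose reduction or discontinuing study treatment", followed by a bracket that refers to 3–5 times ULN or more. The same section states a general purpose: "Tolerance of pirfenidone in addition to baseline transplant medications will be assessed".

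Section 8.1 opens its list of reactions as follows: "The most common adverse reactions (≥10%) are liver problems, photosensitivity, rash, abdominal pain, nausea, vomiting, diarrhea, dyspepsia". It then foresees changes to study drug for several non-hepatic problems:

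- Rash and photosensitivity: "temporary dose reductions, interruptions, or discontinuation of study treatment should be considered".
- Gastrointestinal events: "abdominal pain have occurred with pirfenidone. Temporary dosage reductions or discontinuations may be required".
- QTc between 500 and 550 msec, once confirmed: "verified by a local cardiologist, study treatment should be interrupted". Above 550 msec, the drug is held until the repeat EKG and discontinued if the abnormality persists.

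The second safety endpoint in the synopsis, 4.1 and 10.3 is the number of subjects with drug-related adverse events. Section 10.1, which also presents itself as the list of endpoints, has neither item. It lists permanent discontinuation before 24 weeks and one or more serious adverse events.

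**The concern.** The endpoint has a general name and serves a general purpose, but its definition covers one organ system. An analyst who follows 10.3 to the letter would report a subject taken off the drug for vomiting or rash as not intolerant. The reported count would therefore understate intolerance, in a trial that says it will inform on the tolerance of pirfenidone in transplant recipients who already take several medicines with serious side effects.

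The second problem is that the plan holds two sets of secondary safety endpoints and does not say which governs. Both 10.1 and 10.3 sit in the Data Analysis section, so the choice of which counts are pre-specified could be made after the results are seen.

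**Working it through.** The plan gives no rate, power or precision for intolerance, so there is no stated figure to reproduce. The check compares the sections.

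**Step 1. Which treatment changes foreseen in 8.1 meet the 10.3 definition?**

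| Reason for change | Change foreseen in 8.1 | Intolerance under 10.3? | Counted elsewhere? |
|---|---|---|---|
| Liver tests | Reduction, interruption or permanent stop | Reduction and stop: yes. Temporary interruption: unclear | Related AE; permanent stop in 10.1 |
| Rash, photosensitivity | Reduction, interruption or stop | No | Related AE if so judged; permanent stop in 10.1 only |
| Gastrointestinal | Temporary reduction or discontinuation | No | As above |
| QTc | Interruption, possibly stop | No | As above |

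No endpoint in any list counts a temporary non-hepatic reduction or interruption as intolerance.

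**Step 2. How much of the plan's own reaction list lies outside the definition?** The list in 8.1 splits into:

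- hepatic: 1 (liver problems);
- skin: 2 (photosensitivity, rash);
- gastrointestinal: 5 (abdominal pain, nausea, vomiting, diarrhea, dyspepsia);
- no group-specific text on treatment change: 8 (arthralgia, weight loss, insomnia, sinusitis, anorexia, dizziness, headache, fatigue).

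Total: 1 + 2 + 5 + 8 = 16. Outside the definition: 16 − 1 = 15, or 15/16 = 94%. Among the terms in groups with treatment-change text, 1 + 2 + 5 = 8, of which 2 + 5 = 7 are non-hepatic, or 7/8 = 88%. QTc prolongation is not in the list but has its own interruption rule.

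These are shares of terms. The 10% threshold in 8.1 is a frequency of reactions, not of treatment changes, so it cannot be turned into a number of subjects.

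**Step 3. Illustration with assumed risks.** Let L be the risk of a hepatic treatment change and O the risk of a non-hepatic one, taken as independent. Neither is in the documents. The share of subjects with any change whom 10.3 would count is L / [1 − (1 − L)(1 − O)].

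- L = 3%, O = 30%: 0.03 / 0.321 = 9%, or 0.9 of 9.6 subjects per 30.
- L = 10%, O = 10%: 0.10 / 0.19 = 53%, or 3.0 of 5.7 subjects per 30.

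These are the extremes over L from 3% to 10% and O from 10% to 30%. They show how the loss depends on the two risks and do not estimate it for this trial.

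**Step 4. Do the endpoint lists agree?**

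| Secondary safety item | Synopsis | 4.1 | 10.1 | 10.3 |
|---|---|---|---|---|
| Treatment intolerance | yes | yes | no | yes |
| Drug-related AEs | yes | yes | no | yes |
| Permanent discontinuation | no | no | yes | no |
| One or more SAEs | no | no | yes | no |

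Section 10.1 shares 0 of its 2 items with the other lists, giving 4 distinct items in all. The FEV1 and FVC endpoints are common to all four.

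**Minor wording point.** The second row of the liver table in 8.1 reads "≤5 x ULN accompanied by symptoms or hyperbilirubinemia (>2x ULN") and sets no lower transaminase limit. The bracket in 10.3 about 3–5 times ULN or more does not clearly cover that row. No effect on a count is claimed.

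**The case against.** The strongest reply is that little goes unrecorded. A drug-related rash or gastrointestinal event that leads to a dose change is counted as a related adverse event. A permanent stop for any cause is counted if 10.1 applies, and 11.2.2 requires the actions taken to be described for every adverse event. Tolerance is not one of the three Specific Aims, and 10.3 does not say that the intolerance endpoint alone will assess it. On this view a hepatic measure carries too general a name, and renaming it would be enough. The two lists also overlap in substance: a permanent hepatic stop falls under both, and reporting all four counts would settle the matter.

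Part of this stands. No information is lost, the shares of terms do not measure patients, and the four counts do not exclude one another.

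The core is not removed. The related-event count treats mild nausea and nausea that forces a dose cut alike, so it does not measure tolerance. Its definition in 10.3 also ends in an unresolved alternative based on laboratory tests and physical examination. Permanent discontinuation appears only in the list that conflicts with the other three. Renaming alone would leave the stated tolerance purpose without a matching measure.

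Two criticisms of a broader definition are fair. It would count holds for unrelated illness and short holds pending a repeat EKG. It must also say how failure to complete the 14-day titration is treated.

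**Conclusion.** The concern holds. As written, the 10.3 rule under-counts treatment intolerance: it excludes every non-hepatic treatment change, although 8.1 foresees such changes in three non-hepatic groups (skin, gastrointestinal, QTc). By the plan's own list, 15 of 16 common reactions cannot qualify even when they lead to a change in study drug. The number of subjects missed and any effect on the difference between arms cannot be derived from the documents.

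The conflict between 10.1 and the other lists is a plain inconsistency, with no safety item in common.

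Both should be fixed, but the reach is limited. These are secondary counts with no stated test, and the primary endpoint and sample size do not depend on them. The conclusion rests on the text alone, reading intolerance in the general sense that its name and the stated purpose in 10.3 suggest.

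**What to change.** Before unblinding:

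1. Use one list of secondary safety endpoints in the synopsis, 4.1, 10.1 and 10.3.
2. Define treatment intolerance as any reduction, interruption or permanent discontinuation of study drug made because of an adverse event of any organ system over the 24 weeks, counted by arm. Show the hepatic and drug-related subsets.
3. Do not count reductions made only for a drug interaction, even when the infection being treated is recorded as an adverse event. The case in 8.1 is "With the use of ciprofloxacin at a dosage of 750 mg twice daily, reduce pirfenidone to 534 mg three times a day".
4. State whether failure to reach full dose during titration because of an adverse event counts as a reduction.
5. Reconcile the ULN bracket and the treatment-change terms in 10.3 with the liver table in 8.1. No clinical rule needs to change for this.

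If a purely hepatic endpoint is intended, it should be named as such and a general tolerance count added beside it.

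The cost is protocol and SAP wording, plus a small data-collection change if the adverse event form, which is not in the documents, does not already code the action taken as reduced, interrupted or permanently discontinued and separate interaction-led reductions. For subjects already enrolled, missing codes would be completed from source records. No new visit or test is needed. The downside is that interruptions for events the drug did not cause will also count; the drug-related subset makes that visible.

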11. SAFETY REPORTING OF ADVERSE EVENTS

11.1 Assessment of safety

Specification of Safety Variables

Safety assessments will consist of monitoring and reporting adverse events (AEs) and serious adverse events (SAEs) per protocol. This includes all events of death, and any study specific issue of concern.

Adverse Events

An AE is any unfavorable and unintended sign, symptom, or disease temporally associated with the use of an investigational medicinal product (IMP) or other protocol-imposed intervention, regardless of attribution.

This includes the following:

- AEs not previously observed in the subject that emerge during the protocol-specified AE reporting period, including signs or symptoms associated with CLAD that were not present prior to the AE reporting period.
- Complications that occur as a result of protocol-mandated interventions (e.g., invasive procedures such as cardiac catheterizations).
- If applicable, AEs that occur prior to assignment of study treatment associated with medication washout, no treatment run-in, or other protocol-mandated intervention.
- Preexisting medical conditions (other than the condition being studied) judged by the investigator to have worsened in severity or frequency or changed in character during the protocol-specified AE reporting period.

Serious Adverse Events

An AE should be classified as an SAE if the following criteria are met:

- It results in death (i.e., the AE actually causes or leads to death).
- It is life threatening (i.e., the AE, in the view of the investigator, places the subject at immediate risk of death. It does not include an AE that, had it occurred in a more severe form, might have caused death.).
- It requires or prolongs inpatient hospitalization.
- It results in persistent or significant disability/incapacity (i.e., the AE results in substantial disruption of the subject's ability to conduct normal life functions).
- It results in a congenital anomaly/birth defect in a neonate/infant born to a mother exposed to the IMP.
- It is considered a significant medical event by the investigator based on medical judgment (e.g., may jeopardize the subject or may require medical/surgical intervention to prevent one of the outcomes listed above).

11.2 Methods And Timing For Assessing And Recording Safety Variables

The investigator is responsible for ensuring that all AEs and SAEs that are observed or reported during the study are collected and reported to the FDA, appropriate IRB(s), and Genentech, Inc. in accordance with CFR 312.32

11.2.1 Adverse Event Reporting Period

The study period during which all AEs and SAEs must be reported begins after informed consent is obtained and initiation of any study procedures and ends 30 days following the last administration of study treatment or study discontinuation/termination, whichever is earlier. After this period, investigators should only report SAEs that are attributed to prior study treatment.

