4. EXPERIMENTAL DESIGN

4.1 ENDPOINTS

Primary:

- Change in functional small airways disease (fSAD) as measured by parametric response mapping (PRM) at 24 weeks by treatment arm

Secondary:

- Change in FEV₁ over 24 weeks by treatment arm
- Change in FVC over 24 weeks by treatment arm
- Number of subjects with treatment intolerance over 24 weeks
- Number of subjects with adverse events related to treatment with Pirfenidone

Exploratory:

- Change in bronchoalveolar lavage (BAL) mesenchymal colony forming units (CFUs) by treatment arm
- Change in fibrotic phenotype of BAL mesenchymal cells (expression of collagen, alpha smooth muscle actin, beta-catenin, fibronectin) by treatment arm

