5.2 Baseline Assessment (Visit 1, Week 0)

At the time of baseline, the coordinator will document the following:

- Vital signs (weight, temperature, blood pressure, heart rate, respiratory rate, pulse oximetry)
- Physical exam including general appearance, HEENT, cardiovascular, pulmonary, abdominal, neurologic, dermatologic, and musculoskeletal exams
- Current medications
- Safety blood work for renal and liver evaluation
 - AST, ALT, AP, total bilirubin, creatinine
- Review bronchoscopy results (if performed)
- ECG
- Perform spirometry
- Undergo an HRCT scan with inspiratory and expiratory image acquisition (if HRCT was not done in preceding 6 weeks)
- Serum pregnancy test (if applicable)
- Review adverse events

5.3 Visits 2, 3, 5, 6 (Weeks 4, 8, 16, 20): may be performed at study center or by local lab draw in conjunction with phone visit

- Safety labs to monitor renal and liver function AP, ALT, AST, total bilirubin, creatinine
- Review hospitalizations
- Review medication compliance
- Review concomitant medications
- Review adverse events

5.4 Visit 4 (Week 12):

- Vital Signs (weight, temperature, blood pressure, heart rate, respiratory rate, pulse oximetry)
- Physical exam including general appearance, HEENT, cardiovascular, pulmonary, abdominal, neurologic, dermatologic, and musculoskeletal exams
- Safety blood work for renal and liver evaluation
 - o AP, ALT, AST, total bilirubin, creatinine
- Spirometry
- ECG
- Review hospitalizations
- Review medication adherence
- Review concomitant medications
- Review adverse events
- 5.5 Visit 7 (Week 24):
 - Vital Signs (weight, temperature, blood pressure, heart rate, respiratory rate, pulse oximetry)
 - Physical exam including general appearance, HEENT, cardiovascular, pulmonary, abdominal, neurologic, dermatologic, and musculoskeletal exams Safety blood work for renal and liver evaluation

- o AP, ALT, AST, total bilirubin, creatinine
- Spirometry
- ECG
- HRCT scan
- Review hospitalizations
- Review medication adherence
- Review concomitant medications
- Review adverse events
- Collect unused study medication and return to investigational pharmacy
- Bronchoscopy with consent of patient and primary physician if no contraindication identified

5.6 Visit 8 (Week 28) (Phone visit):

At the 28 week phone visit, the coordinator will:

- Review hospitalizations
- Review adverse events
- Collect vital status

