5.7 Early discontinuation

All subjects will be followed until study completion unless consent to do so is specifically withdrawn by the subject. If study treatment is discontinued, participants will be asked to continue with study assessments as planned including the HRCT at week 24 as per protocol.

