5.8 Randomization

This is a randomized, double-blind, placebo-controlled multi-center study. Assignment to study treatment will be blinded to the study subjects, investigational site personnel, study vendors, and the Sponsor study team, except for the delegated personnel who will review and check the randomization and drug allocation for accuracy.

All patients will be randomized at the Baseline visit, using stratified block randomization with undisclosed block sizes. The stratification factor is FEV1 first vs concurrent FEV1 and FVC decline at time of CLAD onset. Our statistician, [name], will assist with randomization. She will provide the Research Pharmacy (via email) with randomization codes for two separate strata as mentioned above. Within each stratum the statistician will indicate treatment assignment"Active Pirfenidone" or "Placebo" and treatment label ID number. The Research Pharmacist (RP) will be told upon patient entry the stratum to which the patient belongs, identifying the appropriate randomization list for each patient. The RP will then dispense Active or Placebo based on the randomization code on the randomization list. The RP will refer to the randomization code at each dispensing.

In the event of a medical emergency in which breaking the blind is required to provide medical care to the subject, the investigator may obtain treatment assignment directly from the study statistician for that subject.

Visit	Screening ^A	1 Baseline	2 ^B +/- 7days	3 ^B +/- 7days	4 +/- 14day	5 ^B +/- 7days	6 ^B +/- 7days	7 EOT +/-	8 EOS +/-
					S			14day s	7days
Week	-6 - 0	0	4	8	12	16	20	24	28 ^c
Inclusion/exclusion criteria	х								
Informed consent	Х								
Randomization		Х							
Demographics	Х								
Vital Signs	Х	Х			Х			х	
Physical exam	Х	Х			Х			х	
Medical history	х	х							
Adverse events	х	х	Х	х	х	х	х	х	х
Non-elective hospitalizations		х	x	x	x	х	х	х	x
Medication Compliance			Х	х	х	х	х	х	
Concomitant medications	X	x	х	x	x	х	x	х	
Pregnancy test ^D		Х							
Standard of care labs	x	x	х	х	х	х	х	х	
including									
immunosuppressive									
drug levels									
Safety labs (LFTs) ^F	Х	Х	Х	Х	Х	Х	Х	Х	
Spirometry	Х				Х				
Full PFTs		Х						Х	
HRCT ^G		Х						Х	
EKG		Х			Х			Х	
Bronchoscopy with BAL ^H	x	x						х	
Vital status assessment									х

Table 1. Schedule of Assessments

A The time period between the screening and enrollment visit may be up to 6 weeks

B Weeks 4, 8, 16, 20: Laboratory testing may be performed locally

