10. DATA ANALYSIS

10.1 Overview

Our Endpoints are:

Primary:

- Change in functional small airways disease (fSAD) as measured by parametric response mapping (PRM) at 24 weeks by treatment arm

Secondary:

- Change in FEV₁ over 24 weeks by treatment arm
- Change in FVC over 24 weeks by treatment arm
- Number of subjects permanently discontinuing study medication before 24 weeks
- Number of subjects with one or more serious adverse events

Exploratory:

- Change in bronchoalveolar lavage (BAL) mesenchymal colony forming units (CFUs) by treatment arm
- Change in fibrotic phenotype of BAL mesenchymal cells (expression of collagen, alpha smooth muscle actin, beta-catenin, fibronectin) by treatment arm

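### Section 11.2.1 stops all-cause AE/SAE reporting 30 days after last dose, although early stoppers stay under review to week 28, and the SAE endpoint in 10.1 has no counting window

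*Combined protocol and SAP*

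**What the plan says.** **Reporting period.** Section 11.2.1 opens the period after consent and the start of study procedures. It "ends 30 days following the last administration of study treatment or study discontinuation/termination, whichever is earlier". It then adds: "After this period, investigators should only report SAEs that are attributed to prior study treatment". Section 11.1 uses the same period in describing what an AE includes, and section 11.3.2(b) ties all-cause death reporting to it.

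**Follow-up of subjects who stop treatment.** Section 5.7 follows every subject to study completion unless consent is withdrawn. For those off treatment, "participants will be asked to continue with study assessments as planned including the HRCT at week 24 as per protocol". Section 5.6 ("At the 28 week phone visit, the coordinator will") lists review of hospitalizations and adverse events and collection of vital status. In Table 1 the rows for adverse events and "Non-elective hospitalizations" are both marked through week 28.

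**Other reporting text.** Section 11.2 makes the investigator responsible for ensuring that "all AEs and SAEs that are observed or reported during the study are collected and reported". Section 11.3.2(f) applies an attribution-only rule to SAEs arising once a subject has completed or left study participation. The Adverse Event Reporting item of 11.3.2 allows 30 calendar days from awareness for sending unrelated SAEs to the company, with no cut-off tied to last dose.

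**Endpoint.** Section 10.1 lists "Number of subjects with one or more serious adverse events" with no period; the discontinuation endpoint just above it is limited to the time before 24 weeks. The synopsis and sections 4.1 and 10.3 list treatment-related events instead (4.1: "Number of subjects with adverse events related to treatment with Pirfenidone"), also without a period.

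**The concern.** A subject who stops drug at week 8 leaves the 11.2.1 period on day 86 but is still asked about adverse events and hospitalizations up to day 196. Suppose an SAE not attributed to treatment occurs on day 120. The visit schedule will bring it to light, 11.2.1 does not call for it to be reported, and 10.1 does not say whether it counts. The same trial therefore allows two SAE counts.

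If the 11.2.1 period is taken as the counting window, exposure to being counted depends on how long a subject stays on drug. That is a post-randomisation outcome which treatment may influence: section 8.1 provides for permanent discontinuation on certain liver findings, and 10.1 makes permanent discontinuation an endpoint. If more subjects stopped early in one arm, that arm would have less time in which an unattributed SAE or death could be counted, and could look safer for that reason alone.

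**Working it through.** The plan has no figure of its own to reproduce on this point. The check is a day count from the documents, then an illustration on assumed inputs.

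**1. Days covered (no assumed rates).** Take first dose as day 0, week 28 as day 7 × 28 = 196, and the end of the period as last-dose day + 30. The period formally opens at consent, up to 6 weeks before baseline; that time is left out because it precedes treatment.

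| Last dose | Period ends (day) | Uncovered to day 196 | Share of 196 days | Share of 168 days (week 24) |
|---|---|---|---|---|
| Week 4 | 28 + 30 = 58 | 138 | 70% | 65% |
| Week 8 | 56 + 30 = 86 | 110 | 56% | 49% |
| Week 12 | 84 + 30 = 114 | 82 | 42% | 32% |
| Week 20 | 140 + 30 = 170 | 26 | 13% | 0% |
| Week 24 | 168 + 30 = 198 | 0 | 0% | 0% |

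Completers are covered to day 198, past the nominal week-28 contact. Only subjects whose last dose falls before day 196 − 30 = 166 have an uncovered interval.

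**2. Effect on an SAE count (assumed inputs).** The documents give no SAE risk, stopping rate, stopping time or attribution share. Assume the same constant hazard in both arms and let

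- S = 28-week SAE risk,
- d = share of an arm that stops,
- w = days covered for a stopper,
- a = share of later SAEs attributed to treatment, and so still reported.

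Then:

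- P(SAE counted, stopper) = 1 − (1 − S)^((w + a(196 − w))/196)
- Arm proportion = (1 − d)S + d × P
- SE of the difference = √(p₁(1 − p₁)/30 + p₀(1 − p₀)/30)

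Example: S = 30%, stopping 30% vs 10%, all at week 6 (w = 42 + 30 = 72), a = 0.

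- P = 1 − 0.7^(72/196) = 12.3%
- Arm with more stopping: 0.7 × 30% + 0.3 × 12.3% = 24.7%
- Other arm: 0.9 × 30% + 0.1 × 12.3% = 28.2%
- Difference 3.5 points, ratio 0.87, or 1.1 subjects in 30
- SE 11.4 points, so the difference is 3.5/11.4 = 0.31 of one SE

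**3. Sensitivity.**

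- With a = 25% or 50%, the 3.5 points fall to 2.6 or 1.7.
- With a 24-week window and the same hazard (S = 1 − 0.7^(168/196) = 26.3%): 22.1% vs 24.9%, 2.8 points, 0.8 subject, SE 10.9 points.
- Over a grid with S = 20%, 30% or 50%, stopping 20%, 30% or 40% vs 10%, at week 4, 6, 8 or 12, and a = 0, the smallest difference is 0.8 points (0.2 subject) and the largest 9.4 points (2.8 subjects). Relative to its own SE, the difference runs from 0.08 to 0.74.
- Equal stopping at the same times gives zero. Swapping the arms reverses the sign (28.2/24.7 = 1.14).

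**The case against.** The best defence is that 11.2.1 governs reporting while the visit schedule governs collection. On that view AE review to week 28 is already provided for, and 11.2.1 limits only what goes onward. Section 11.2 is no obstacle: it can be read as a general duty whose timing its own subsection, 11.2.1, supplies, so I do not rest the point on a contradiction between the two. A window of last dose + 30 days is also a legitimate exposure-based count. And section 11.3.2(f), with the timeline for unrelated SAEs, can be read as keeping unattributed SAEs reportable while a subject is still in the study.

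Much of this stands, but it does not close the gap. Sections 11.1 and 11.3.2(b) carry the reporting period into the description of an AE and into death reporting, so its reach is wider than onward transmission. If 11.3.2(f) and the unrelated-SAE timeline do keep such events reportable, they disagree with the second sentence of 11.2.1, and the sections still need reconciling. On any of these readings the 10.1 endpoint lacks a window.

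Two further points are fair. The SAE endpoint does not carry the by-arm wording used for FEV₁ and FVC, and no test of SAEs is described, so the distortion concerns a descriptive comparison. The phrase about whichever is earlier can also be parsed in two ways; under either, a subject who stops drug but stays in the study is cut off no later than 30 days after last dose.

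A reader might infer that the plan fixes the counting window at last dose + 30 days and so builds in a bias that favours pirfenidone. The documents do not support that. No section makes 11.2.1 the counting window, and none gives stopping or SAE rates by arm.

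**Conclusion.** The point holds as a minor one. As written, 11.2.1 gives early stoppers a shorter period of all-cause reporting than completers, which does not fit the follow-up in sections 5.6 and 5.7 and Table 1 and fits poorly with 11.3.2(f) and the unrelated-SAE timeline. Separately, the SAE endpoint in 10.1 has no stated window.

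The day counts follow from the documents, but they describe uncounted time only if the 11.2.1 period is adopted as the window. The between-arm distortion also needs unequal stopping and rests wholly on assumed inputs: about one subject per arm of 30 in the example, and below one standard error throughout the grid. Its direction is unknown. The treatment-related AE endpoint is less exposed, because attributed SAEs remain reportable after the period ends. Nothing here touches the primary fSAD endpoint, the power table or the sample size.

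**What to change.** 1. **Recording.** Reconcile sections 5.6, 5.7, 11.2.1 and 11.3.2 (item f and the Adverse Event Reporting item) and Table 1. State that AEs and SAEs, whatever their attribution, are recorded in the study data for every randomised subject through the week-28 contact, whether or not treatment has stopped, unless consent to follow-up is withdrawn.
2. **Counting.** In 10.1, count the SAE endpoint by randomised arm over one fixed window from randomisation: week 28, or week 24 to match the neighbouring endpoints. A last-dose + 30-day count alongside is optional.
3. **Unchanged.** The timelines for onward reporting to the company and regulators can stay as they are.

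The cost is about one sentence in 11.2.1 and one in 10.1, with the related items aligned to them. AE review, hospitalization review and vital status already run to week 28, so no visit is added. The downside is a few more events to record.
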